#### **10.12.3. *Laboratory Variables***

The following haematology, biochemistry, coagulation, viral serology and urinalysis parameters (as shown within the protocol) will be included within subject listings (and presented in the units as shown) and summary tables where relevant:

- Haematology: platelet count ( $\times 10^9/L$ ), white blood cell (WBC) count (absolute) ( $\times 10^9/L$ ), neutrophils (absolute) ( $\times 10^9/L$ ), lymphocytes (absolute) ( $\times 10^9/L$ ), monocytes (absolute) ( $\times 10^9/L$ ), eosinophils (absolute) ( $\times 10^9/L$ ), basophils (absolute) ( $\times 10^9/L$ ), red blood cell (RBC) count ( $\times 10^{12}/L$ ), haemoglobin (g/L).
  - Note: Complete blood count differentials are collected for this study but will only be listed and not included in any summaries, with the exception of the eosinophils differential which will be summarised as a biomarker (see [Section 10.11.1](#)).
- Biochemistry: sodium (mmol/L), potassium (mmol/L), glucose (mmol/L), albumin (g/L), chloride (mmol/L), bicarbonate (mmol/L), calcium (mmol/L), total protein (g/L), creatinine (umol/L), total bilirubin (umol/L), direct bilirubin (umol/L), phosphorus (mmol/L), alkaline phosphatase (ALP) (IU/L), alanine transaminase (ALT) (IU/L), aspartate transaminase (AST) (IU/L), urea (mmol/L), Total creatinine kinase (IU/L), HDL (mmol/L), Total Cholesterol (mmol/L), Triglycerides (mmol/L), C-reactive protein (mg/L).
- Coagulation: prothrombin time (PT) (secs), activated partial thromboplastin time (APTT) (secs), International normalised ratio.

- Other: HIV-1 and HIV-2 antibodies, hepatitis B surface antigen (HbsAg), hepatitis C antibodies (HCAb), FSH (IU/L), beta HCG (qualitative), QuantiFERON-TB Gold/Tuberculosis.
- Urinalysis: Specific gravity, pH, blood, protein, glucose, bilirubin, white blood cells, ketones, nitrites.
- Urinalysis (microscopy): Urine RBC (/HPF), Urine WBC (/HPF), Hyaline Casts, Cellular Casts, Granular Casts, Urine Culture.

Laboratory data collected in different units to that shown will be converted to the above specified units (if possible) for presentation in subject Listings.

Summary statistics for absolute and changes from baseline by timepoint, including pre-baseline timepoints, will be tabulated, by treatment group, for haematology, biochemistry and coagulation). Baseline here will be the last non-missing measurements taken prior to the first dose of study treatment. Shift tables will also be presented for the shift from baseline to above, below, or within normal range at each visit. Any scheduled pre-baseline data will also be summarized by visit and treatment group.

Categorical urinalysis parameter (not including microscopy, specific gravity or pH) will be summarized at each visit by the number and percentage of subjects having results in each category.

Laboratory parameters (Haematology, Biochemistry, Coagulation, Human Immunodeficiency Virus, Hepatitis A, B and C, Urinalysis and Urinalysis (microscopy) where done) will be included in subject listings. Laboratory values outside the normal range will be identified in subject listings as above or below the normal range.

Unscheduled visit assessments will be included within subject listings.

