5.4.6 Clinical Laboratory Assessments

Clinical laboratory assessments include haematology, blood chemistry, and urinalysis as listed in Table 10. Subjects will have fasted (except for water) for a minimum of 9 hours prior to these assessments. On dosing days, samples will be collected pre-dose. All laboratory test results must be reviewed by the Investigator or qualified designee.

Table 10 Clinical Laboratory Tests^a

Haematology	Chemistry	Urinalysis	Infectious Disease
Complete Blood Count	Sodium	Specific gravity	HIV
Automated differential ^b	Potassium	pH	Hepatitis B
PT, aPTT, and INR ^c	Chloride	Blood	Hepatitis C
	Bicarbonate	Protein	QuantiFERON®-TB Gold
	Urea	Glucose	
	Creatininine	Bilirubin	
	Total protein	WBC	
	Albumin	Ketones	
	Calcium	Nitrites	
	Phosphorus	Microscopic examination ^d	
	Glucose	Drug, nicotine, cotinine	Miscellaneous
	Total creatininine kinase		FSH ^e
	AST (SGOT)		Total IgE
	ALT (SGPT)		Pregnancy test (Section 5.4.7)
	Alkaline phosphatase		C-reactive protein
	Total bilirubin		Alcohol breath or urine test
	Direct bilirubin		
	HDL		
	Total cholesterol		
	Triglycerides		

ALT=alanine aminotransferase; aPTT=activated partial thromboplastin time, AST=aspartate aminotransferase; FSH=follicle stimulating hormone, HDL=high density lipoprotein; HIV=human immunodeficiency virus; IgE=immunoglobulin E, INR=international normalized ratio, PT=prothrombin time, SGOT=serum glutamic oxaloacetic transaminase; SGPT=serum glutamic pyruvic transaminase; TB=tuberculosis; WBC=white blood cell.

^a Chemistry and urinalysis panels may be changed depending upon the clinical laboratory's standard panels.

^b Eosinophil number from the complete blood count differential will be used for the eosinophil endpoint.

^c Coagulation will only be performed at Visit 1 and at the Final visit.

^d Microscopic examination will only be triggered if urine result is abnormal for blood, WBC, nitrites and/or protein.

^e All females who are eligible based upon post-menopausal criteria as per Section 4.8.4.

Clinical laboratory assessments will be conducted on visit days detailed Table 4 through Table 9 in Section 3.3.

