9.2 Sample Size Determination

The primary objective of the study is to assess the safety and tolerability of UPB-101 when administered as multiple ascending doses. A sample size of 40 subjects with 8 subjects per cohort (6 on active drug + 2 on placebo) is considered sufficient to meet this goal. The sample size is not based on formal statistical hypothesis testing.

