9.4.6 Safety Analyses

All safety analyses will be conducted using the Safety Population.

MedDRA will be used to code verbatim terms of AEs. Adverse events will be summarized by system organ class, preferred term, and treatment group for the number and percent of subjects reporting AEs, the number of events, and the number of subjects with any AE. All AEs will be listed, including onset and resolution dates, verbatim term, preferred term, treatment, severity, relationship to treatment, action taken, and outcome. The pooled placebo group will be used in these summaries.

Absolute values and change from baseline physical examinations, clinical laboratory evaluations vital signs assessments, and ECG parameters will be summarized by visit and by treatment group. The frequency of subjects with safety laboratory results outside of normal reference ranges will be tabulated by treatment and visit. No inferential statistical analyses are planned for safety parameters. Placebo groups will not be pooled in these summaries.

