## 7. STUDY ENDPOINTS

### 7.1. Primary Endpoint

The primary endpoints are AEs, SAEs, physical examinations, clinical laboratory assessments, vital signs, and electrocardiograms (ECGs). Subject withdrawals, early terminations, and dosing compliance are also assessed. These endpoints are evaluated in the Safety Population.

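### As written, SAP 10.12.3 keeps absolute neutrophil, lymphocyte, monocyte and basophil counts out of the haematology tables that protocol 9.4.6 requires, and Section 11 does not declare it

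*SAP*

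**What the plan says.** SAP 7.1 and protocol section 2 both make clinical laboratory assessments part of the primary endpoint. Protocol 5.4.6 (Table 10) puts "Automated differential" in the haematology column of the safety panel.

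For analysis, protocol 9.4.6 states that "clinical laboratory evaluations vital signs assessments, and ECG parameters will be summarized by visit and by treatment group". Its next sentence adds a tabulation, by treatment and visit, of subjects with laboratory results outside the reference range. Neither sentence makes an exception for white cell subsets.

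SAP 10.12.3 names nine haematology parameters for listings and, where relevant, for summary tables. The five white cell subsets are each marked as absolute counts. A note directly beneath says: "Complete blood count differentials are collected for this study but will only be listed and not included in any summaries". The note exempts eosinophils only and sends them to the biomarker section (10.11.1). Later in 10.12.3, summary statistics and shift tables are promised for haematology in general, without mention of the note.

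**The concern.** A specific exclusion ordinarily overrides a general rule. A programmer following 10.12.3 literally would leave four cell types out of both haematology tables, although the protocol promised those tables for the whole safety panel. SAP section 4 says that deviations from protocol-specified analyses will be listed in Section 11. Section 11 records three changes: the refined PK and PD populations, the single formal analysis, and the dropped cytokines. This is not among them.

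White cell subsets are reasonable safety data for this product. The protocol describes an antibody that inhibits dendritic-cell-mediated CD4+ T-cell differentiation (1.2), lists immunologic response among the risks to be minimised (Table 3), and makes severe infections an adverse event of special interest (8.7). The documents name no neutrophil or lymphocyte signal, so the relevance is inferred from the mechanism. Total white cell count can stay flat while its components move in opposite directions, and a by-subject listing shows neither a mean change nor a shift against placebo.

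**Working it through.** No sample size, power or alpha figure is involved. Protocol 9.4.6 says: "No inferential statistical analyses are planned for safety parameters". The check is a comparison of texts and a count of parameters.

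**Step 1. What does the word differential refer to?** There are two candidates: the cell counts themselves, or percentages of total white cells.

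- Protocol Table 10, footnote b: "Eosinophil number from the complete blood count differential will be used for the eosinophil endpoint". Here the differential is the source of a cell number.
- Protocol 6.1.2 says that absolute eosinophil numbers come from the automated complete blood count, which includes a differential count of white cells.
- The SAP note's own exception is the eosinophil differential, summarised as a biomarker. By the two protocol sections above, that biomarker is an absolute number. If the word meant a percentage, the exception would not describe the endpoint it points to.
- The SAP 10.12.3 haematology list contains no percentages, and the note sits immediately under the absolute counts.

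The first reading fits all four texts better.

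**Step 2. Count the parameters on that reading.**

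| Parameters named in SAP 10.12.3 | Number | Haematology summary and shift tables (14.3.3.1, 14.3.3.2) | Summarised elsewhere |
|---|---|---|---|
| Platelets, WBC, RBC, haemoglobin | 4 | Yes | – |
| Eosinophils | 1 | No | Yes, as a biomarker in the PD Population |
| Neutrophils, lymphocytes, monocytes, basophils | 4 | No | No |
| Total | 9 | 4 | 1 |

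So 4 of 9 parameters are summarised nowhere. With the four counts restored, the haematology tables would carry 4 + 4 = 8 of 9.

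**Step 3. Does anything else in the SAP restore them?** The general haematology sentence in 10.12.3 and the two table titles name no subset and do not lift the note. The list of tables in 13.2 has no separate differential table.

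**Step 4. Does protocol versioning explain it?** The SAP is written to protocol version 8.0. The only version 9.0 change logged for section 9.4.6 is removal of the MedDRA version, so the laboratory rule was not altered.

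**Step 5. What routes remain for these cells?**

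- Total WBC stays in both haematology tables.
- Values outside the normal range are marked in listings (SAP 10.12.3), and listings are ordered by treatment group (SAP 13.1).
- Laboratory abnormalities judged clinically significant are reported as adverse events (protocol 8.8), and these are tabulated against pooled placebo (9.4.6). This route is open for neutrophils and lymphocytes. Protocol 5.4.6 withholds monocyte and basophil results from sites after screening, so it is largely closed for those two.

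**The case against.** The strongest reply is that the note means percentages only. The parent bullet already names the four counts, marks each as absolute, and allows summary tables for them. A note saying that differentials are also collected would be redundant if it meant the counts just listed, but natural if it meant something additional. The general summary sentence and the table titles are unrestricted. The table shells in SAP Section 14, which would show the exact contents, are not in the text available for review. This reading is possible, and on it there is no departure from the protocol for the four counts. It is still the weaker reading, because it cannot accommodate the eosinophil exception. Even if it was intended, the sentence needs rewording so that nobody programs it the other way.

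A second reply is that little is lost. By-subject review is feasible with 24 to 40 subjects. Each cohort has 6 active and 2 placebo subjects, so five cohorts give 5 × 6 = 30 active and 5 × 2 = 10 placebo. Protocol 9.4.6 does not pool placebo for laboratory summaries, so the placebo column could hold only 2 subjects per cohort, although SAP 10.1.3 generally pools. This limits how informative the tables would be. It does not replace a tabulation that the protocol promises.

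A reader might go further and infer that part of the primary safety question goes unanswered, or that a fall in neutrophils or lymphocytes would go unseen. The documents do not support that. The results are collected, listed and flagged, and clinically significant neutrophil or lymphocyte abnormalities can reach the adverse event tables. Nor is a formal comparison with placebo lost, since none was planned.

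**Conclusion.** The point holds as an undeclared narrowing of a protocol-specified descriptive analysis. On the better-supported reading, 4 of the 9 named haematology parameters, all part of the primary laboratory endpoint, lose their change-from-baseline and shift tables at every haematology visit. The loss is of the side-by-side tables by treatment group, not of the data.

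This rests on reading differential as the cell counts and on the shells in Section 14 not saying otherwise. The effect is greatest for monocytes and basophils, where adverse event reporting by sites is unlikely to fill the gap. The point should be corrected before the tables are run, but it does not undermine the trial's safety conclusions.

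**What to change.** Reword the note in SAP 10.12.3 to say three things:

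1. Only percentage differentials, if received from the laboratory, are listing-only.
2. Absolute neutrophil, lymphocyte, monocyte and basophil counts are included in Tables 14.3.3.1 and 14.3.3.2.
3. Eosinophils continue to be summarised as a biomarker under 10.11.1.

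Simply deleting the note would be worse, because it would remove both the rule for percentages and the eosinophil cross-reference.

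If the sponsor does intend to leave the four counts out of the tables, Section 11 should declare and justify that as a change from protocol 9.4.6.

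The cost is one SAP sentence and four more parameters in table programs already planned. No new data collection is needed.

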1.8.6 Minimization of Risks in Study

Based on available non-clinical data, as well as known adverse effects of currently available biologic disease-modifying asthma agents, several potential risks have been identified for which mitigation actions have been developed to minimize the relevant risks in clinical studies of UPB-101. In addition, AE monitoring and other routine clinical and laboratory monitoring (including laboratory safety such as haematology and biochemistry, vital signs, physical examination, and ECGs) will be conducted.

To ensure subjects’ safety, the protocol outlines the dose escalation process and dose stopping rules to be followed. Subjects will be followed for at least 12 weeks in consideration of the half-life of UPB-101 and to ensure adequate follow-up for immunogenicity monitoring. Subjects who have persistent anti-UPB-101 antibodies will continue to be evaluated until the level of these antibodies show evidence of declining, are no longer detectable, and/or are deemed to be of no clinical relevance. Based on the target organs of toxicity identified in the toxicology studies, the risk minimization actions that will be included in clinical studies are presented in Table 3.

Table 3 Risk Minimization Actions Based on Non-clinical Toxicology Studies

Target Organs	Theoretical/Potential Risks	Risk Minimization Action
Renal/Urinary System	Occult blood observed in urine of 1 animal at █ mg/kg in the 4-week repeat dose toxicity study. Results were not reproduced in the 13- or 26-week repeat dose toxicity study at the same dose level.	Measurement of standard blood biochemistry and urinalysis during the Screening Period to exclude subjects with abnormal renal function and during the Dosing and Observation Periods to assure subject safety. Positive results from urinalysis will be confirmed with a microscopic examination.
Immunologic Response	Perivascular inflammatory cell infiltration in several organs as well as inflammatory cell infiltration in the alveoli and bronchioles associated with changes in blood chemistry including high globulin and γ -globulin ratio. Immune complex deposition in tissues was not demonstrable.	Standard safety monitoring and 12 weeks of immunogenicity follow-up.

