14.3.2.1.2	Treatment Emergent Adverse Events by System Organ Class and Preferred Term up to Week 24 – Safety Population	X	
14.3.2.1.3	Treatment Emergent Adverse Events by System Organ Class, Preferred Term and Severity up to Week 24 – Safety Population	X	
14.3.2.1.4	Treatment Emergent Adverse Events Related to IMP by System Organ Class and Preferred Term up to Week 24 – Safety Population	X	
14.3.2.1.5	Treatment Emergent Adverse Events of Special Interest by System Organ Class and Preferred Term up to Week 24 – Safety Population	X	
14.3.2.1.6	Treatment Emergent Serious Adverse Events by System Organ Class and Preferred Term up to Week 24 – Safety Population	X	X
14.3.2.1.7	Treatment Emergent Adverse Events Leading to Discontinuation of Investigational Product by System Organ Class and Preferred Term up to Week 24 – Safety Population	X	

Table Number	Table Title	Final	Admin Analysis
14.3.2.1.8	Treatment Emergent Adverse Events Leading to Withdrawal from the Study by System Organ Class and Preferred Term up to Week 24 – Safety Population	X	X
14.3.2.2.1	Overall Summary of Treatment Emergent Adverse Events Over Entire Study Period – Safety Population	X	
14.3.2.2.2	Treatment Emergent Adverse Events by System Organ Class and Preferred Term Over Entire Study Period – Safety Population	X	
14.3.2.2.3	Treatment Emergent Adverse Events by System Organ Class, Preferred Term and Severity Over Entire Study Period – Safety Population	X	
14.3.2.2.4	Treatment Emergent Adverse Events Related to IMP by System Organ Class and Preferred Term Over Entire Study Period – Safety Population	X	
14.3.2.2.5	Treatment Emergent Adverse Events of Special Interest by System Organ Class and Preferred Term Over Entire Study Period – Safety Population	X	
14.3.2.2.6	Treatment Emergent Serious Adverse Events by System Organ Class and Preferred Term Over Entire Study Period – Safety Population	X	
14.3.3.1	Haematology Parameters Summary – Safety Population	X	
14.3.3.2	Haematology Parameters: Shift of Normal Range – Safety Population	X	
14.3.4.1	Biochemistry Parameters Summary – Safety Population	X	
14.3.4.2	Biochemistry Parameters: Shift of Normal Range – Safety Population	X	
14.3.5.1	Coagulation Parameters Summary – Safety Population	X	
14.3.5.2	Coagulation Parameters: Shift of Normal Range – Safety Population	X	
14.3.6	Urinalysis Parameters: Summary – Safety Population	X	
14.3.7	Vital Signs Parameters Summary – Safety Population	X	

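### The planned urinalysis tables cannot show how many subjects in each treatment group became newly positive for urine blood after dosing

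*SAP*

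**What the plan says.** Clinical laboratory assessments are part of the primary endpoint (Protocol Section 2, SAP 7.1). For these, Protocol 9.4.6 states: "Absolute values and change from baseline physical examinations, clinical laboratory evaluations vital signs assessments, and ECG parameters will be summarized by visit", with a split by treatment group. It also asks for the frequency of out-of-range results by treatment and visit.

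SAP 10.12.3 divides the panels. Absolute values and changes from baseline "will be tabulated, by treatment group, for haematology, biochemistry and coagulation", and the shift-table sentence stands in the same paragraph. Urinalysis has its own sentence: "Categorical urinalysis parameter (not including microscopy, specific gravity or pH) will be summarized at each visit by the number and percentage of subjects" in each category. Microscopy goes to the listings only. The table list in SAP 13.2 agrees: its single urinalysis entry is Table 14.3.6, "Urinalysis Parameters: Summary – Safety Population".

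Protocol Table 3 (Section 1.8.6) has one row for the renal and urinary system. The finding is "Occult blood observed in urine of 1 animal at" a redacted dose in the 4-week study, followed by "Results were not reproduced in the 13- or 26-week repeat dose toxicity study at the same dose level". The action is blood biochemistry and urinalysis at screening and during the study, and "Positive results from urinalysis will be confirmed with a microscopic examination". Protocol Table 10 makes microscopy a reflex test: "Microscopic examination will only be triggered if urine result is abnormal for blood, WBC, nitrites and/or protein".

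**The concern.** Urine blood is the only renal or urinary finding that the protocol carries over from toxicology. Of the four safety laboratory panels, the one that measures it gets the thinnest summary. A count at each visit does not link a subject's results over time. It mixes subjects who were positive before dosing with those who turned positive afterwards, and it cannot separate one persistently positive subject from several subjects each positive once. Results confirmed by microscopy are not separated from unconfirmed ones.

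At stake is whether the study report can state, from a table, how many subjects on UPB-101 and on placebo developed new urine blood, and in how many of them microscopy supported it.

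**Working it through.** The plan gives no figure to reproduce. The check has two parts: which outputs exist, and what by-visit counts can reveal.

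**Outputs in SAP 13.2**
- Haematology: summary 14.3.3.1, shift 14.3.3.2.
- Biochemistry: summary 14.3.4.1, shift 14.3.4.2.
- Coagulation: summary 14.3.5.1, shift 14.3.5.2.
- Urinalysis: summary 14.3.6, no shift. No table covers microscopy.

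**Inputs**
- Group size (SAP Section 8): 6 active and 2 placebo per cohort. Pooled placebo is 5 × 2 = 10 if all five cohorts run.
- Baseline: urinalysis at Visits 1 and 2 and on Day 1 before dosing.
- Post-baseline urinalyses, counting Day 15 from Protocol Table 5:
  - Table 6 schedule: Days 15, 29, 36, 57, 71, 85, 113, 141, 225 = 9.
  - Table 7 schedule: Days 15, 29, 57, 85, 113, 141, 225 = 7.
  - Table 8 schedule: Days 15, 29, 57, 85, 113, 141, 169, 197, 225 = 9.
- The seven Table 7 days are common to all three schedules.

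**Distinct subjects ever positive.** Let c be the number positive at each visit in a group of n. The number of distinct subjects D lies between max(c) and min(n, sum of c). Suppose, for illustration, one positive result per visit and no missing samples.
- Active group, n = 6, nine visits: D runs from 1 to min(6, 9) = 6. With seven visits it runs from 1 to min(6, 7) = 6.
- Pooled placebo, n = 10, seven common days: D runs from 1 to min(10, 7) = 7.

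Every active-group visit shows 1/6 = 16.7%, while the subject incidence can be anything from 1/6 = 17% to 6/6 = 100%.

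**New positives when Day 1 is also tabulated.** Let b be the number positive at baseline. New positives then lie between max(0, D − b) and min(D, n − b). Take n = 6, b = 1 and one positive at each of nine later visits.
- Same subject throughout: D = 1, so 1 − 1 = 0 new positives.
- Later positives spread over the other five subjects: 5 new positives, the maximum, since 6 − 1 = 5.

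Both cases give the same Table 14.3.6.

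**Why confirmation matters.** The documents give no background rate of dipstick positivity. Assume a rate r per visit, independent between visits. The chance of at least one positive in nine visits is 1 − (1 − r)^9: 24% at r = 3%, 37% at 5% and 61% at 10%. Under these assumptions a count of ever-positive subjects contains substantial noise, so it needs the placebo group, baseline status and microscopy beside it.

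**The case against.** A reader might infer that treatment-emergent haematuria is never counted by arm. The documents do not support that. Summary tables are presented by treatment group (SAP 10.1.3), so dipstick blood appears by group at each visit. An isolated abnormality that the investigator judges clinically significant is reported as an adverse event (Protocol 8.8). Such events are counted by subject and treatment group in Tables 14.3.2.1.2 and 14.3.2.2.2. That route is incomplete, because Protocol 8.2 excludes abnormal values that are not clinically significant.

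A reader might also infer an established renal risk. Table 3 reports one animal, not reproduced in two longer studies, under a column for theoretical or potential risks. The action it describes is monitoring of individual subjects, not a promised table. The biochemistry half of that action, which includes creatinine and urea, does get change-from-baseline and shift tables.

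A third inference is that the SAP plainly breaks Protocol 9.4.6. For dipstick categories that goes too far: a difference from baseline is not defined for them, 9.4.6 does not mention shift tables, and the by-visit layout fits its out-of-range sentence. What stands is that a shift is the natural categorical counterpart of the change from baseline that 9.4.6 calls for, and the other three panels have one. Specific gravity and pH are numeric and also get no summary.

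Finally, baseline prevalence can be read from the same table, and the within-subject link can be recovered from Listing 16.2.8.2.4, which is ordered by treatment group, subject and visit. Both points are correct. The first does not identify new positives, as the calculation shows. The second is workable with 6 active subjects per cohort, and is the main reason why the gap is minor.

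**Conclusion.** The point holds in limited form and is minor. The planned laboratory tables cannot give, by treatment group, the number of distinct subjects negative for urine blood at baseline and positive after dosing, with or without microscopic support. In the illustration, one unchanged table fits 0 to 5 new positives in a group of 6. Cases reported as adverse events are counted; the rest need a hand count from the listings.

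This rests on the SAP 13.2 table list being complete. The shells in SAP Section 14 are not in the available text, so the layout of Table 14.3.6 could not be checked. The visit-by-visit results in the illustration and the 3% to 10% background rates are assumptions. No safety conclusion depends on a formal test, so nothing else in the analysis is affected.

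**What to change.** Add one table to SAP 10.12.3 and 13.2, in the Safety Population by treatment group, through Week 24 and through Week 32:

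1. Shift from baseline (last non-missing result before first dose) to worst post-baseline dipstick category for urine blood.
2. Number of subjects newly positive, meaning negative at baseline and positive at any time after dosing.
3. Number of those newly positive subjects whose reflex microscopy red cell result was above the laboratory reference range. Use all subjects with a post-baseline urinalysis as the denominator, because microscopy is done only when triggered. Neither document gives a red cell threshold, so the criterion must be written down.

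A footnote should say whether unscheduled repeats count towards the worst value, since SAP 10.1.1 otherwise leaves that to the blinded data review meeting. A matching shift for urine protein is not needed on this argument.

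The cost is one extra table from data already collected and a short SAP wording change. No visit, sample or clinical rule changes.
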